10.2. Planned Interim Analyses

A blinded interim safety and PK analysis is planned for this study to analyze all PK, ADA, and MNA samples for Cohorts 1-3 through Day 60 and Day 120. A second blinded interim safety analysis is planned to analyze all PK, ADA, and MNA samples for Cohort 4 through Day 90. Stopping criteria are for safety and are defined in section 9.5.

10.3. Final Analysis Plan

The ICH Guidance Document E9 (Statistical Principles for Clinical Trials) will be followed for all statistical content. For categorical data, summaries of frequencies and percentages will be presented. Summaries for continuous data will include minimum, lower quartile, median, mean, standard deviation, upper quartile, and maximum.

10.3.1. Analysis Populations

All subjects who received study product will be included in the safety population and analyzed as treated. The PK analysis population will consist of all subjects who complete G03-52-01 injection and have sufficient evaluable PK samples for the estimation of PK parameters.

10.3.2. Demographics and Baseline Characteristics

Subject demographics and baseline characteristics will be summarized by dose cohort and control group.

10.3.3. Safety Analysis Plan

10.3.3.1. Adverse and Serious Adverse Events

AEs will be coded using Medical Dictionary for Regulatory Activities® (MedDRA). All AEs that occur after the initiation of study medication will be summarized using frequency counts and percentages. Summaries will be presented by dose cohort and control group. The following summaries will be presented for AEs and SAEs:

- Overall (i.e., regardless of severity or relationship to treatment)
- By severity grade (mild, moderate, or severe)
- By relationship to study medication
- By MedDRA level hierarchy (system organ class and preferred term)

Unless otherwise specified, at each level of subject summarization in reporting the incidence of the AEs, a subject will be counted once if the subject reported one or more events. If more than

one occurrence of an event is reported, the event of the worst severity or the worst-case relationship assessment will be summarized.

10.3.3.2. Additional Safety Analyses

Vital signs, physical examinations, and clinical laboratory values, including change from baseline, will be summarized by dose cohort and control group.

Descriptive summary statistics for laboratory data at admission (baseline value) and each applicable post-injection visit, including change from the baseline value, will be calculated. Descriptive summary statistics for vital signs at screening (baseline value) and each applicable post-injection visit, including change from the baseline value, will be calculated. Shift tables, showing individual subject changes from baseline will be presented for laboratory parameters using toxicity grading (Appendix B). Subjects with Graded values of vital sign and laboratory parameters will be identified in listings.

10.3.4. PK Analysis Plan

PK parameters will be estimated for each of the six monoclonal antibodies separately using noncompartmental methods in WinNonlin or a similar software package. Parameters will be estimated by dose cohort. Summary statistics will include the mean, median, coefficient of variation, and range. When evaluable, estimated PK parameters will include:

- $AUC_{(0-t)}$: Area under the concentration time-curve to the last concentration above the lower limit of quantitation
- C_{max} : Maximum observed concentration
- T_{max} : Time of maximum observed concentration
- K_{el} : Elimination rate constant
- $AUC_{(0-\infty)}$: Area under the concentration time-curve extrapolated to infinity
- $t_{1/2}$: Terminal elimination half-life
- CL : Total clearance
- V_z : Volume of distribution

Additionally, multi-compartmental models will be considered based on inspection of concentration-time curves. If models are fit, base models will assume first-order elimination from the central compartment, and models will be parameterized in terms of clearance, volume of distribution and inter-compartmental rates. Standard objective goodness of fit measures will be used to determine the final model.

10.3.5. Immunogenicity

Immunogenicity will be measured by the development of antibody titers. The presence of ADA will be measured over the course of the post-injection period.

10.3.6. Missing values and outliers

All attempts will be made to collect all data per protocol. No imputation will be performed for missing values. Outliers identified during the PK analysis will be discussed in the analysis report.

11. SOURCE DOCUMENTS AND ACCESS TO SOURCE DATA/DOCUMENTS

The site will maintain appropriate medical and research records for this trial, in compliance with ICH E6(R2) GCP, Section 4.9, and regulatory and institutional requirements for the protection of confidentiality of subjects. As part of participating in a DOD-affiliated, or manufacturer-sponsored study, the site will permit authorized representatives of the sponsor(s), DOD, and regulatory agencies to review (and, when required by applicable law, to copy) clinical records for the purposes of quality assurance reviews, audits, and evaluation of the study safety and progress.

Forms for use as source documents will be derived from the electronic CRFs and will be provided by ICON. Additional source data are all information, original records of clinical findings, observations, or other activities in a clinical trial necessary for the reconstruction and evaluation of the trial. Examples of these original documents and data records include, but are not limited to, hospital records, clinical and office charts, laboratory notes, memoranda, pharmacy dispensing records, recorded data from automated instruments, copies or transcriptions certified after verification as being accurate and complete, microfiches, photographic negatives, microfilm or magnetic media, x-rays, and subject files and records kept at the pharmacy, laboratories, and medico-technical departments involved in the clinical trial. If data is recorded directly into the eCRF with no paper source, then that data should be listed as being a direct electronic data entry with no paper source available.

12. QUALITY CONTROL AND QUALITY ASSURANCE

Following a written DOD-accepted site quality management plan, the investigational site is responsible for conducting routine quality assurance and quality control activities to internally monitor study progress and protocol compliance. The PI will provide direct access to all trial-related sites, source data/documents, and reports for the purpose of monitoring and auditing by the sponsor, and inspection by local and regulatory authorities. The PI will ensure all study personnel are appropriately trained and applicable documentations are maintained on site.

Clinical monitors will verify that the clinical trial is conducted, and data are generated, documented (recorded), and reported in compliance with the protocol, GCP, and the applicable regulatory requirements. Clinical monitoring reports will be submitted to Ology Bioservices.

ICON will implement quality control procedures beginning with the data entry system and generate data quality control checks that will be run on the database. Any missing data or data anomalies will be communicated to the site(s) for clarification and resolution.

13. ETHICS/PROTECTION OF HUMAN SUBJECTS

13.1. Ethical Standard

The investigator will ensure that this study is conducted in full conformity with principles of the Belmont Report: Ethical Principles and Guidelines for the Protection of Human Subjects of Research of the National Commission for the Protection of Human Subjects of Biomedical and Behavioral Research (April 18, 1979) and codified in 45 CFR 46, 21 CFR 50 and 56, and ICH E6(R2); 62 Federal Regulations 25691 (1997), if applicable. The investigator's Institution will hold a current Federal Wide Assurance (FWA) issued by the Office of Human Research Protection for federally funded research.

13.2. Institutional Review Board

The site will provide for the review and approval of this protocol and the associated informed consent documents, by an appropriate ethics review committee or IRB listed on the FWA. Any amendments to the protocol or consent materials must also be approved before they are placed into use unless change is for the safety of the subject. Only those IRB members who are independent of the investigators and the sponsor should provide an opinion on study related matters. Verification of IRB approval of the protocol and the written informed consent will be transmitted by the investigator or designee prior to the shipment of study product. No deviations from or changes to the protocol will be initiated without prior approval of an appropriate amendment unless change is for the safety of the subject.

13.3. Informed Consent Process

13.3.1. Informed Consent

The written consent document will embody the elements of informed consent as described in the Declaration of Helsinki and will adhere to the ICH Harmonized Tripartite Guideline for Good Clinical Practice. Informed consent should be implemented before any protocol-specified procedures or interventions are carried out. Informed consent will be obtained in accordance with 21 CFR 50.25 and 45 CFR 46. Information should be presented both orally and in written form.

An investigator or designee will describe the protocol to potential subjects face-to-face. The Subject Information and Consent Form may be read to the subjects, but, in any event, the investigator shall give the subjects ample opportunity to inquire about details of the study and ask any questions before the signing and dating the consent form.

Study staff must inform subjects that the trial involves research, and explain the purpose of the trial, those aspects of the trial that are experimental, any expected benefits, all possible risks (including a statement that the particular treatment or procedure may involve risks to the subject or to the embryo or fetus, if the subject is or may become pregnant, that are currently unforeseeable), the expected duration of the subject's participation in the trial, the procedures of

the research study, including all invasive procedures, and the probability for random assignment to treatment groups. Subjects will be informed that they will be notified in a timely manner if information becomes available that may be relevant to their willingness to continue participation in the trial. They must also be informed of alternative procedures that may be available, and the important potential benefits and risks of these available alternative procedures. Subjects must receive an explanation as to whether any compensation and any medical treatments are available if injury occurs, and, if so, what they consist of, or where further information may be obtained. Subjects must be informed of the anticipated financial expenses, if any, to the subject for participating in the trial, as well as any anticipated prorated payments, if any, to the subject for participating in the trial. They must be informed of whom to contact (e.g., the investigator) for answers to any questions relating to the research project. Information will also include the foreseeable circumstances and/or reasons under which the subject's participation in the trial may be terminated. The subjects must be informed that participation is voluntary and that they are free to withdraw from the study for any reason at any time without penalty or loss of benefits to which the subject is otherwise entitled.

Neither the investigator, nor the trial staff, should coerce or unduly influence a subject to participate or continue to participate in the trial. The extent of the confidentiality of the subjects' records must be defined, and subjects must be informed that applicable data protection legislation will be followed. Subjects must be informed that the monitor(s), auditors(s), IRB, DOD, Ology Bioservices, and regulatory authority(ies) will be granted direct access to the subject's original medical records for verification of clinical trial procedures and/or data without violating the confidentiality of the subject, to the extent permitted by the applicable laws and regulations, and that, by signing a written informed consent form, the subject is authorizing such access. Subjects must be informed that records identifying the subject will be kept confidential, and, to the extent permitted by the applicable laws and/or regulations, will not be made publicly available and, if the results of the trial are published, the subject's identity will remain confidential.

Consent forms must be in a language fully comprehensible to the prospective subjects. Informed consent shall be documented by the use of a written consent form approved by the IRB and signed and dated by the subject and the person who conducted the informed consent discussion. The signature confirms that the consent is based on information that has been provided and all questions have been answered to the prospective participant's satisfaction. Each subject's signed informed consent form must be kept on file by the investigator for possible inspection by Regulatory Authorities and/or the sponsor and Regulatory Compliance persons. The subject should receive a copy of the signed and dated written informed consent form and any other written information provided to the subjects and should receive copies of any signed and dated consent form updates and any amendments to the written information provided to subjects.

13.4. Exclusion of Women, Minorities, and Children (Special Populations)

Children are excluded for safety reasons.

13.5. Subject Confidentiality

Subject confidentiality is held strictly in trust by the participating investigators, their staff, and the sponsor and their agents. This confidentiality is extended to cover testing of biological samples in addition to the clinical information relating to participating subjects.

The study protocol, documentation, data, and all other information generated will be held in strict confidence. No information concerning the study, or the data will be released to any unauthorized third party without prior written approval from the sponsor.

The study monitor or other authorized representatives of the sponsor may inspect all documents and records required to be maintained by the Investigator, including, but not limited to, medical records (office, clinic, or hospital) and pharmacy records for the subjects in this study. The clinical study site will permit access to such records.

13.6. Study Discontinuation

Ology Bioservices has the right to terminate this study or the site's participation at any time. Reasons for terminating the study may include, but are not limited to, the following:

- Incidence or severity of adverse events indicates a potential health hazard;
- Data recording is inaccurate or incomplete;
- Investigator does not adhere to the protocol or applicable regulatory guidelines in conducting the study.

13.7. Future Use of Stored Specimens

Samples will be collected as outlined in the protocol. Subjects will be given a choice during the informed consent process to have their residual linked samples stored indefinitely for future research, have their residual samples de-linked from any subject information and stored indefinitely, or have their residual linked samples destroyed at completion of the study. The use of long-term stored linked samples will be conducted under the restrictions regarding confidentiality, as outlined in the preceding paragraphs.

Only coded specimens will be sent to the sponsor with the code identifiers maintained by the principal investigator. Any future research studies will utilize only the residual long-term stored specimens from subjects consenting to future use.

14. DATA HANDLING AND RECORD KEEPING

The investigator is responsible to ensure the accuracy, completeness, legibility, and timeliness of the data reported. All data collection forms should be completed in a neat, legible manner to ensure accurate interpretation of data. Black ink is required to ensure clarity of reproduced copies. When making changes or corrections, cross out the original entry with a single line, and initial and date the change. **Do not erase, overwrite, or use correction fluid or tape on the original.**

Copies of the electronic CRF (eCRF) will be provided for use as source documents and maintained for recording data for each subject enrolled in the study. Data reported in the eCRF derived from source documents should be consistent with the source documents or the discrepancies should be explained.

Ology Bioservices and/or its designee will provide guidance to investigators on making corrections to the data collection forms/source documents and eCRFs.

14.1. Data Management Responsibilities

All source documents and laboratory reports must be reviewed by the clinical team and data entry staff, who will ensure that they are accurate and complete. Adverse Events must be graded, assessed for severity and causality, and reviewed by the site Principal Investigator or designee.

Data collection is the responsibility of the clinical trial staff at the site under the supervision of the site Principal Investigator. During the study, the investigator must maintain complete and accurate documentation for the study.

ICON will serve as the Statistical and DCC for this study, and will be responsible for data management, quality review, analysis, and reporting of the study data.

14.2. Data Capture Methods

Clinical data (including AEs, concomitant medications, and reactogenicity data) and clinical laboratory data will be entered into a 21CFR11-compliant Internet Data Entry System provided by ICON. The data system includes password protection and internal quality checks, such as automatic range checks, to identify data that appear inconsistent, incomplete, or inaccurate. Clinical data will be entered directly from the source documents.

14.3. Types of Data

Data for this study will include clinical safety assessments, safety laboratory assessments, immunology and PK.

14.4. Timing/Reports

A final report will be prepared following the availability of all the safety and immunogenicity data.

14.5. Study Records Retention

Study files (except for future use consent forms) must be maintained for a minimum of two years after the last approval of a marketing application in an ICH region and until there are no pending or contemplated marketing applications in and ICH region or at least 2 years have elapsed since the formal discontinuation of clinical development of the investigational product. These documents should be retained for a longer period, however, if required by local regulations. No records will be destroyed without the written consent of the sponsor, if applicable. It is the

responsibility of the sponsor to inform the investigator when these documents no longer need to be retained. Consent forms for future use will be maintained as long as the sample exists.

14.6. Protocol Deviations

A protocol deviation is any noncompliance with the clinical trial protocol, GCP, or protocol-specific MOP requirements. The noncompliance may be either on the part of the subject, the investigator, or the study site staff. As a result of deviations, corrective actions are to be developed by the site and implemented promptly.

These practices are consistent with ICH E6(R2):

- 4.5 Compliance with Protocol, Sections 4.5.1, 4.5.2, and 4.5.3
- 5.1 Quality Assurance and Quality Control, Section 5.1.1
- 5.20 Noncompliance, Sections 5.20.1, and 5.20.2.

It is the responsibility of the site PI/study staff to use continuous vigilance to identify and report deviations within five working days of identification of the protocol deviation, or within five working days of the scheduled protocol-required activity. All deviations must be promptly reported to ICON/Ology Bioservices.

All protocol deviations, as defined above, must be addressed in study subject source documents. A completed copy of the Protocol Deviation Form must be maintained in the Regulatory File, as well as in the subject's source document. Protocol deviations must be sent to the local IRB/IEC per their guidelines. The site PI/study staff is responsible for knowing and adhering to their IRB requirements.

15. PUBLICATION POLICY

All manuscripts resulting from this trial will be reviewed by representatives from the sites, DOD and the product manufacturer. Each institution will have at least thirty days to review the publication prior to submission.

The International Committee of Medical Journal Editors (ICMJE) member journals have adopted a trials-registration policy as a condition for publication. This policy requires that all clinical trials be registered in a public trials registry such as ClinicalTrials.gov, which is sponsored by the National Library of Medicine (NLM). Other biomedical journals are considering adopting similar policies. This trial will be registered in NLM in accordance with the new NLM requirements under the Food and Drug Administration Amendments Act (FDAAA).

*Journal Citation :

APPENDIX A: SCHEDULE OF EVENTS

Study Visit	Screening ¹	Baseline	03	04	05 Cohort 1-3 Only	06	07	08	09	10	11	12	13 / Early Term	14 Cohort 4 Only
Study Day (Window)	-28 to -3	0	24 hr	48 hr	72 hr	4	8±1	15±1	30±1	45±3	60±3	90±3	120±3	180±3
Review Inc/ Excl Criteria	X	X												
Review Medical History	X	X												
Review Contraception/menses	X													
Perform Abbreviated PE ³	X	X												
Perform Symptom-Directed PE ¹³		X	X	X	X	X	X	X	X	X	X	X	X	X
Obtain Vital Signs ⁴	X	X	X	X	X	X	X	X	X	X	X	X	X	X
Obtain Screening Labs ⁵	X													
Obtain Clinical Safety Labs ⁶		X				X	X	X					X ¹⁸	X
Serum β-HCG	X ⁷													
Urine pregnancy test		X			X				X				X ¹⁸	X
Urine Dipstick ⁸	X	X											X ¹⁸	X
Urine Toxicology	X	X												
Breathalyzer test	X	X												
Immunogenicity (ADA) ¹⁴		X				X	X	X	X	X	X	X	X	X
Hypersensitivity Panel ¹⁵		X												
12-lead ECG ⁹	X													
Viral Serology ¹⁰	X													
PK samples ¹¹		X	X	X	X	X	X	X	X	X	X	X	X	X
MNA		X ¹⁶			X			X	X ¹⁷	X	X	X	X	X
Concomitant Medications ²	X	X	X	X	X	X	X	X	X	X	X	X	X	X
Randomization		X												
Study Drug Administration		X												
Future Use Sample ¹²		X				X		X						

Study Visit	Screening ¹	Baseline 01	Baseline 02	03	04	05 Cohort 1-3 Only	06	07	08	09	10	11	12	13 / Early Term	14 Cohort 4 Only
Study Day (Window)	-28 to -3	0	24 hr	48 hr	72 hr	4	8±1	15±1	30±1	45±3	60±3	90±3	120±3	180±3	
Counsel on the avoidance of pregnancy	X		X	X	X	X	X	X	X	X	X	X	X	X	X
Counsel on avoidance of botulinum toxin and vaccines	X		X	X	X	X	X	X	X	X	X	X	X	X	X
AE Review		X	X	X	X	X	X	X	X	X	X	X	X	X	X
SAE Review		X	X	X	X	X	X	X	X	X	X	X	X	X	X

1. Screening will be completed within 28 days prior to administration of study drug and may require more than one visit.
2. Concomitant medications including all of the following: prescription drugs, over-the –counter drugs, herbs, vitamins, nutritional supplements, illicit and recreational substance use, birth control information.
3. PE includes height and weight at screening.
4. Vital Signs to include sitting diastolic and systolic blood pressure, heart rate, and oral temperature. Vital signs will be checked just before injection and every visit.
5. Subjects should be fasting for Screening Laboratory Tests that will include hemoglobin, WBC with differential, absolute neutrophil count and platelet count. MCV, MCH, MCHC, RDW, MPV, which are included in a complete blood count with differential, will not be graded, serum creatinine, BUN, calcium, total bilirubin, direct bilirubin, indirect bilirubin, alkaline phosphatase, PT, PTT, INR, ALT, AST, sodium, potassium, and total CK. Subjects in cohort 4 only will have NX02 levels drawn at screening
6. Subjects should be fasting for Clinical Safety Laboratory Tests that will include hemoglobin, WBC with differential, absolute neutrophil count and platelet count. MCV, MCH, MCHC, RDW, MPV, which are included in a complete blood count with differential, will not be graded, serum creatinine, BUN, calcium, total bilirubin, direct bilirubin, indirect bilirubin, alkaline phosphatase, PT, PTT, INR, ALT, AST, sodium, potassium, and total CK.
7. A serum pregnancy test will be obtained for all women of reproductive capacity. Results must be confirmed as negative before study product is dosed.
8. A urine dipstick will be done to evaluate for presence of protein, glucose or blood in urine. If dipstick is abnormal, a complete urinalysis with microscopic will be performed.
9. A 12-lead ECG will be done during screening.
10. Viral Serology includes HIV, HBsAg and antibody to HCV.
11. Subjects in Cohorts 1-3 will have PK samples taken at the following times: pre-dose, 2, 4, 8, 24, 48, and 72 hours post injection and on days 4, 8, 15, 30, 45, 60, 90, and 120. Subjects in Cohort 4 will have PK samples taken at pre-dose, 6 hours post-dose, and on days 1, 2, 4, 8, 15, 30, 45, 60, 90, 120, and 180.
12. Serum from subjects who give consent will be stored for future use. On Days 0, 8, and 30.
13. The subject will be under direct observation during at least the initial 30 minutes of the injection. A physical examination will be performed at approximately 30 minutes after starting the injection and again in response to subject symptoms which will include the following: General appearance including alertness and any difficulty breathing, HEENT, Chest, Heart, Skin and Joints.
14. Draw prior to dosing at baseline for all Cohorts. Subjects in Cohorts 4 will not have ADA blood draws on Day 15 or Day 30. Cohort 4 will have ADA drawn on follow- up Days 45, 60, 90, 120 and 180.
15. The Hypersensitivity Panel includes cytokine and complement panels, IgE, and tryptase. Draw 14ml prior to dosing. If a subject develops anaphylaxis or anaphylactoid reaction, an additional 14 mL sample will be drawn during the event and another will be drawn after the event.
16. MNA: To be drawn pre-dose for All Cohorts. Cohort 4 subjects will also have a 2-hour post dose optional (+/- 10 minutes) draw.
18. Cohorts 1-3 only.

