- One female subject experienced mild lightheadedness during infusion

NTM-1632 dose level 0.33mg/kg

- One female subject experienced mild loose stools 1-day post infusion

Risk Factors Associated with Monoclonal Antibodies

Injections of mAbs may be associated with injection reactions including: anaphylaxis/anaphylactoid type reaction, especially during a first exposure, and when administered rapidly. Fever, chills and rigors, typically occurring within the first two hours following injection, characterize these reactions. Other symptoms sometimes associated with injection reactions include nausea, vomiting, rash, pruritus, bronchospasm or other acute pulmonary response, angioedema, hypotension, hypertension, cardiac arrhythmias, dizziness, dyspnea, headache, and malaise.

Risk of Immunogenicity

Antibodies directed against G03-52-01 may develop following injection. This will be assessed by taking blood samples at selected visits throughout the study. G03-52-01 is a fully humanized mAb which based on experience with other humanized or chimeric mAbs, reduces the immunogenic potential.

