6.3. Vital Signs

Vital sign assessments including systolic and diastolic blood pressure (BP) [measured after sitting for at least 10 minutes], heart rate (HR), and oral temperature will be performed at each in-clinic study visit. Vital signs that are thought to be aberrant due to an error in measurement may be repeated. During screening and follow-up, a measurement that is a Grade 1 (as referenced in Appendix B Toxicity Grading) may be repeated once if the PI believes a transient condition led to the aberrant value.

Vital signs obtained at screening will serve as baseline values for the subject. Grade 1 values are allowable unless deemed clinically significant by the study investigator.

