7.2. Visit 2: Baseline (Day 0)

Subjects meeting inclusion/exclusion criteria will be admitted to the clinical unit the day of the injection and the following procedures will be performed prior to study drug administration:

- Review inclusion/exclusion criteria to ensure the subject remains eligible for enrollment
- Update medical history
- Review and update concomitant medications
- Perform abbreviated physical examination
- Obtain vital signs
- Perform Breathalyzer test to detect recent alcohol use
- For women, a urine hCG test will be done. The results must be confirmed to be negative before dosing
- Obtain urine sample for toxicology
- Obtain blood samples for
 - Baseline serum PK (prior to injection and at the completion of the injection and 2hr, 4hr, and 8 hr post dosing for subjects in Cohorts 1-3)
 - Baseline serum PK (prior to injection and at 6 hours post-injection for subjects in Cohort 4)
 - Serum sample to store for future use samples (for subjects who consent)
 - MNA (prior to injection for subjects in Cohorts 1-3)

- MNA (prior to injection and at 2 hours post-injection (optional) for subjects in Cohort 4)
- ADA (prior to injection for all subjects)
- Hypersensitivity panel
- Clinical Safety Labs
- Randomize the subject and obtain study product from the pharmacy
- Perform IM Administration of study product
- Assessment of AEs and SAEs after administration of study product
- The subject is eligible for discharge after all assessments have been performed, including the 8-hour post injection blood draw and there are no signs of anaphylaxis.

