7.3. Visit 3: Out-patient Follow-up (24 hours/Day 1)

- Obtain vital signs
- Review and update concomitant medications
- Perform symptom directed PE
- Obtain blood samples for the following:
 - PK measurement at 24 hours (+/- 2 hours)
- Counsel women of child-bearing potential on the avoidance of pregnancy
- Counsel the subject not to receive any botulinum toxin preparation (e.g., Botox) for 4 months after injection.
- Assessment of AEs and SAEs

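### Cheap improvement of modest yield: no vital signs are scheduled between the Day 0 injection and the visit at about 24 hours, although the protocol expects fever, chills and rigors mainly within two hours

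*Protocol*

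**What the plan says.** Protocol Appendix A, footnote 4, and the same footnote to SAP Table 3-2 fix the timing: "Vital signs will be checked just before injection and every visit". Protocol 6.3 gives no time within a visit; it says only that blood pressure, heart rate and "oral temperature will be performed at each in-clinic study visit". Protocol 7.2 lists vital signs once for Day 0, under a heading for pre-dose procedures. That heading alone is not decisive, because the list beneath it also holds post-dose blood draws, but footnote 4 is explicit. The next scheduled set is at Visit 3, about 24 hours after injection (Protocol 7.3).

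On antibody injection reactions, Protocol 2.3.1 says: "Fever, chills and rigors, typically occurring within the first two hours following injection, characterize these reactions". It also names hypotension, hypertension and arrhythmia, without giving them a time of their own.

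After the injection on Day 0 the plan provides direct observation for at least 30 minutes and, in Appendix A footnote 13, "A physical examination will be performed at approximately 30 minutes after starting the injection and again in response to subject symptoms". Protocol 7.2 adds "Assessment of AEs and SAEs after administration of study product". Subjects stay about 8 hours (Protocol 4) and leave only if they show no signs of anaphylaxis (Protocol 7.2).

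Change from baseline in vital signs is part of a primary endpoint (Protocol 3.2.1). SAP 7.22.3 summarizes it at nominal timepoints, in Table 14.3.5.3.

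**The concern.** Fever is detected with a thermometer, and no temperature is scheduled in the two hours when the protocol expects it. Protocol Appendix B grades fever, tachycardia and hypotension, but between injection and about 24 hours the plan asks for no measurement that could be graded. The primary-endpoint summary therefore has no row for the period the protocol itself singles out.

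Off-schedule readings would fill this only in part. If staff took one, it would appear in a listing (SAP 7.1), and a graded value would be identified there (Protocol 10.3.3.2). It would have no nominal time in Table 14.3.5.3, however, and SAP 7.22 lists unscheduled-visit vital signs without summarizing them. What is lost is values that are never measured, together with the summary rows for this period. This is a first-in-human study, and the subjects who might still be reached are in the cohort given its top dose, 100 mg.

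**Working it through.** The plan states no count of vital-sign sets, so there is no figure to reproduce. The check is a count from the visit schedules.

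**Scheduled post-dose sets** (Protocol Summary and Appendix A, one set per visit):
- Cohorts 1-3: 24, 48 and 72 hours, then Days 4, 8, 15, 30, 45, 60, 90 and 120: 3 + 8 = 11.
- Cohort 4: Days 1, 2, 4, 8, 15, 30, 45, 60, 90, 120 and 180: 11.
- All subjects: 30 × 11 + 10 × 11 = 440.

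**Where they fall.** The first is at about 24 hours, or 22 to 26 hours if vital signs follow the ±2-hour window of the Visit 3 PK draw. Sets before that visit: 0 of 11 in both schedules. Sets within two hours of injection: 0.

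**What the 30-minute examination covers.** Footnote 13 lists general appearance, HEENT, chest, heart, skin and joints. Protocol 6.2 describes the heart item as regularity of rhythm. None of these is a reading of temperature, blood pressure or heart rate.

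**Contacts already planned for Cohort 4.** For PK, "Subjects in Cohort 4 will have PK samples taken at pre-dose, 6 hours post-dose" (footnote 11). For the neutralization assay, "Cohort 4 subjects will also have a 2-hour post dose optional (+/- 10 minutes) draw" (footnote 16). With the 30-minute examination and discharge at about 8 hours, these give natural times of 0.5, 2, 6 and 8 hours.

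| Per Cohort 4 subject | As planned | With four readings |
|---|---|---|
| Post-dose sets | 11 | 11 + 4 = 15 |
| Before about 24 h | 0 | 4 |
| Within 2 h | 0 | 2 |
| Longest gap while in clinic | about 8 h | 4 h (2 h to 6 h) |
| Longest gap in first 24 h | about 24 h | 16 h (8 h to 24 h) |

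The successive gaps with the readings are 0.5, 1.5, 4, 2 and 16 hours.

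**Reach.** The 100 mg cohort was added after the Day 60 interim analysis of Cohorts 1-3 (Protocol 2.2), so those cohorts had been dosed. At most Cohort 4 remains, 10 of 40 subjects (25%; 8 active, 2 placebo), plus any replacements. Added sets: 4 × 10 = 40.

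**Expected yield.** Protocol 2.3.1 lists these related events for the two predecessor products: hemoglobin, ALT, urine protein, AST, blood sugar and neutrophils (6), then forehead pressure, lightheadedness and loose stools (3). That is 9 kinds, of which 0 are temperature, blood pressure or heart-rate events.

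**Is Cohort 4 still open?** SAP 2.0 (24 August 2022) is dated 351 days after protocol 3.0 (7 September 2021). One Cohort 4 subject's course takes at most about 28 days of screening + 14 days of cohort dosing + 183 days of follow-up = 225 days. No Cohort 4 dosing date is given, so completed dosing is plausible but not established.

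**The case against.** The strongest reply is that the two-hour statement describes overt reactions. Chills and rigors are noticed by subject and staff, and the plan watches for them by observation, examination, adverse event assessment and a clinical condition on discharge. In each cohort, one active and one placebo sentinel are dosed first, and the other eight wait at least 24 hours (Protocol 4). A pre-dose hypersensitivity sample is held in reserve (Protocol 6.5.3). All of this stands, and it confines the gap to transient changes with few or no symptoms. It does not close it, because none of these steps schedules a temperature, blood pressure or heart-rate reading.

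The manual of procedures, which Protocol 6.2 cites for examination details, may call for readings on Day 0. It is not among the documents. Even if it does, neither the protocol nor the SAP gives such readings a nominal time.

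The amendment may also come too late, and it is not free: both points stand and are reflected in the fix. So does a limit on interpretation. The new rows would set 8 active against 2 placebo subjects, without the placebo pooling of SAP 7.1 and without Cohorts 1-3.

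A reader might infer that injection reactions would go unseen for 24 hours, or that the halting rules cannot work. The documents support neither. Symptomatic reactions are covered as above. Halting criterion 4 (Protocol 8.5.1) needs Grade 3 events in the same class in at least two subjects, and such values would have to pass unnoticed during an attended stay. Nor does the two-hour window clearly extend to blood pressure or rhythm: temperature is the vital sign most directly tied to it.

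**Conclusion.** The gap is real and small. As written, 0 of 11 scheduled post-dose vital-sign sets falls before about 24 hours, in either schedule, for a measure that belongs to a primary endpoint. What can be lost is transient, minimally symptomatic change in temperature, blood pressure or heart rate on Day 0. Nothing in the documents suggests that a safety event was missed, and the predecessor products, reported as generally well tolerated during and after infusion (Protocol 2.2), point to a modest yield.

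The conclusion assumes that footnote 4 means what it says and that no document outside the protocol and SAP schedules further readings. The value of the amendment depends on Cohort 4 or replacement subjects remaining to be dosed. If none remain, only the study-report statement applies.

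**What to change.** For any Cohort 4 or replacement subject not yet dosed, add blood pressure, heart rate and temperature on Day 0 at:
- the examination at about 0.5 hours;
- about 2 hours, with the optional draw or as a separate check if that draw is not taken;
- the 6-hour PK draw;
- about 8 hours, before discharge.

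Measure change from the Day 0 pre-injection reading. This needs stating, because Protocol 6.3, Protocol 10.3.3.2 and SAP 3.17 use screening values, up to 28 days old, while SAP 7.1 uses the latest earlier measurement. SAP 7.1 ties its definition to the dose date rather than the time of injection, so the amendment should name the Day 0 reading explicitly. Amend Appendix A footnote 4, Protocol 7.2, SAP 3.17, SAP Table 3-2 and Table 14.3.5.3 to match.

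For subjects already dosed, state in the study report that the vital-sign summaries do not cover injection to about 24 hours.

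Cost: an amendment with IRB approval before use (Protocol 13.2); new data-entry timepoints; and seated rest of at least 10 minutes before each blood pressure (Protocol 6.3), so 4 × 10 = about 40 minutes per subject within the existing stay. No extra visit or blood is needed. Expect some additional transient Grade 1 values to review.
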